### **10.5.3 Safety Analysis**

Safety analyses in general will be descriptive and will be presented in tabular format with the appropriate summary statistics. Safety analyses will be presented using the Safety Analysis Set, except for the presentation of DLTs, which will use the DLT-Evaluable Set.

The on-treatment period is defined as:

From the start of study treatment, to earlier of (30 days after the last dose of the study treatment, date of first follow-up anticancer therapy -1), inclusive.

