- q 30-day safety follow-up will be performed for at least 30 days after the last study drug administration or before starting new anti-cancer treatment, whichever comes first, as described in Section 7.4.2. If the day of treatment discontinuation is over 30 days from last study drug administration, this follow up visit is not needed.
- r Patients who did not experience progressive disease or death during the 30-day safety follow-up will be followed until the start of a new anti-cancer treatment, progressive disease, death, lost to follow up, withdrawal of consent from any further participation, or at the discretion of the Investigator. Tumor assessment per RECIST v1.1 will be performed at the same frequency as for patients receiving treatment depending on when the discontinuation occurs (i.e., every 6 weeks [ $\pm 7$  days] for the first 36 weeks and, every 9 weeks [ $\pm 7$  days] thereafter). If a new anticancer therapy is planned to start before the next planned tumor assessment, the tumor assessment may be performed just before starting the new therapy.
- s If patient provides consent, samples should be collected prior to study drug infusion. Starting at Cycle 5, Day 1, every 4 cycles thereafter (Cycle 9, Cycle 13, etc.), and at the EOT visit. For patients with suspected or confirmed COVID-19 infections, follow the dose modifications in [Appendix H](#).
- t A washout period of no less than 14 days is required before restarting DS-6157.

*CONFIDENTIAL*

Study Drug: DS-6157a

Sponsor/Innovations Study Numbers: DS6157-A-U101/GI 289

Final Protocol: 17 August 2021 Version 6.0

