- Patient who meets any of exclusion criteria based on the most recent data, or who experienced ILD of any grade or any other dose modification toxicity event during DS-6157a treatment will not be eligible for IPDE.

IPDE may be conducted up to a dose that is 1 dose level below the dose already established to be safe and tolerable. Dose escalation should not be more than 3 dose levels at a time. The actual dose level will be decided based on the overall individual clinical status and PK profile. A patient may be allowed further IPDE after completing a minimum of another 4 cycles after the first IPDE, as long as the conditions for IPDE are met. AEs arising after IPDE should follow dose modifications/reductions per [Table 2](#), but further re-escalations will be prohibited after such events.

Dose can be delayed for up to 28 days from the planned date of administration. If a patient has a persisting AE/SAE that requires a longer dose delay, then patient will be withdrawn from the study after consulting with Medical Monitor.

Treatment cycles for a patient for whom DS-6157a dosing was temporarily withheld for any reason may have future cycles scheduled based on the date of the last DS-6157a dose. However, the tumor assessments will follow the pre-specified schedules relative to the start of the study treatment (Cycle 1 Day 1).

Investigators may contact the Medical Monitor or designee to discuss questions regarding dose modification or discontinuation of study drug.

All confirmed or suspected coronavirus disease 2019 (COVID-19) infection events must be recorded in the eCRF. Please refer to [Appendix H](#) for additional information on dose modifications.

*CONFIDENTIAL*

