	
Evaluations should include:
 
 
• high resolution CT
 
• pulmonologist consultation (infectious Disease consultation as clinically indicated)
 
• blood culture and CBC. Other blood tests could be considered as needed
 
• Consider bronchoscopy and bronchoalveolar lavage if clinically indicated and feasible.
 
• pulmonary function tests and pulse oximetry (SpO2)
 
• arterial blood gases if clinically indicated
 
• one blood sample collection for PK and exploratory biomarker analysis as soon as ILD/pneumonitis is suspected, if feasible.
 
 
Other tests could be considered, as needed.
 
If the AE is confirmed to be ILD/pneumonitis, follow the management guidance as outlined below.
 
All events of ILD/pneumonitis regardless of severity or seriousness will be followed until resolution including after drug discontinuation.

Grade 1	
The administration of DS-6157a must be interrupted for any ILD/pneumonitis events regardless of grade.
 
 
• Monitor and closely follow-up in 2 to 7 days for onset of clinical symptoms and pulse oximetry
 
• Consider follow-up imaging in 1-2 weeks (or as clinically indicated).
 
• Consider starting systemic steroids (e.g. at least 0.5 mg/kg/day prednisone or equivalent) until improvement, followed by gradual taper over at least 4 weeks.
 
• If worsening of diagnostic observations despite initiation of corticosteroids, then follow Grade 2 guidelines.*
 
 
For Grade 1 events, DS-6157a can be restarted only if the event is fully resolved to Grade 0:
 
 
- If resolved in ≤28 days from day of onset, maintain dose
 
- If resolved in >28 days from day of onset, reduce dose
 

	
1 level
 
However, if the event Grade 1 ILD occurs beyond cycle Day 22 and has not resolved within 49 days from the last infusion, the drug should be discontinued.
 
* If patient is asymptomatic, then patient should still be considered as Grade 1 even if steroid treatment is given.

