## 7. STUDY ASSESSMENTS AND EVALUATIONS

### 7.1 Overview

All patients should visit the study center on the days specified within this protocol. The complete Schedule of Assessments for this study is presented at the beginning of this protocol (see [Assessment Schedule](#)). The key procedures required in this study include:

- All AEs regardless of seriousness or relationship to DS-6157a treatment (called study treatment) spanning from the signing of the ICF until at least 30 calendar days after the patient's last dose of study drug, or the patient's start of another cancer treatment are to be recorded on the corresponding screen(s) included in the eCRF.
- PK samples throughout the study
- Baseline and on-treatment blood biomarker and immunogenicity assessments
- Tumor biopsy biomarker assessments
- Tumor assessments (based on computed tomography [CT]/positron emission tomography [PET]/ and/or magnetic resonance imaging [MRI] scan) according to RECIST Version 1.1 ([Appendix B](#)).

A cycle of treatment is scheduled to last 3 weeks (21 calendar days). Multiple procedures may be scheduled at the same time point relative to DS-6157a dosing. Priority must be given to PK collection at the time specified. Vital signs and ECG assessments must be performed prior to PK sample collections when these assessments are scheduled for the same timepoints.

*CONFIDENTIAL*

Study Drug: DS-6157a

Sponsor/Innovations Study Numbers: DS6157-A-U101/GI 289

Final Protocol: 17 August 2021 Version 6.0

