#### **10.5.3.1 Adverse Events and DLTs**

Safety will be assessed through the analysis of the reported incidence of treatment-emergent AEs (TEAEs). Treatment-emergent AEs are those with an onset date during the on-treatment period.

Adverse events will be graded according to NCI [CTCAE Version 5.0](#) and coded using the current version of Medical Dictionary for Regulatory Activities (MedDRA; <https://www.meddra.org/>).

DLTs in the DLT Evaluable Set will be listed and summarized.

Treatment-emergent AEs will be summarized using system organ class (SOC) and preferred term. In addition, treatment-emergent SAEs, TEAEs by maximum NCI CTCAE grade, and TEAEs associated with study treatment discontinuation, reduction or interruption will also be presented.

All AEs will be listed including, but not limited to, verbatim term, preferred term, SOC, NCI CTCAE grade, and relationship to study drug.

Deaths will be listed and summary tables will be generated.

SAEs starting or worsening after the on-treatment period, if reported as related to study treatment, will be summarized.

Adverse events of special interest (AESIs) once defined based on continued review of the safety profile of DS-6157a will also be summarized.

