### **11.2.2 Reporting of Adverse Events**

All AEs regardless of seriousness or relationship to DS-6157a treatment (called study treatment), spanning from the signing of the ICF until 30 calendar days after discontinuation or completion of study treatment as defined by the study for that patient after his/her last dose of study drug, are to be recorded on the corresponding screen(s) included in the eCRF.

All AEs resulting in discontinuation from the study should be followed until resolution or stabilization. All new AEs occurring during this period must be reported and followed until resolution unless, in the opinion of the Investigator, the AE or laboratory abnormality/ies is/are not likely to improve because of the underlying disease. In this case, the Investigator must record his or her reasoning for this decision in the patient’s medical record.

After 30 days after completion of protocol-specific treatment or discontinuation, only AEs, SAEs, or deaths assessed by the Investigator as treatment-related are to be reported.

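### A new adverse event 31 to 49 days after the last infusion is a TEAE if the patient is re-dosed, but not if it ends treatment

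*Combined protocol and SAP*

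**What the plan says.** Section 10.5.3 of the protocol opens the on-treatment period at the first dose and runs it "to earlier of (30 days after the last dose of the study treatment, date of first follow-up anticancer therapy -1), inclusive". Section 10.5.3.1 adds: "Treatment-emergent AEs are those with an onset date during the on-treatment period". It gives no other route to TEAE status. The tables by preferred term, by maximum grade, and of events tied to stopping, reducing or interrupting treatment are all tables of TEAEs. The laboratory shift table in Section 10.5.3.2 uses the worst value on treatment, so it inherits the same end date.

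Section 6 allows treatment to pause for longer than that period: "Dose can be delayed for up to 28 days from the planned date of administration". Past that limit, "If a patient has a persisting AE/SAE that requires a longer dose delay, then patient will be withdrawn from the study", after the Medical Monitor has been consulted. Table 2 has a matching rule for Grade 1 ILD. If an event arising late in the cycle "has not resolved within 49 days from the last infusion, the drug should be discontinued". Footnote q of the Assessment Schedule provides for a late stop: "If the day of treatment discontinuation is over 30 days from last study drug administration, this follow up visit is not needed".

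The AE collection wording is not uniform. Sections 3.3, 7.1, 7.4.2 and 11.4 count 30 days from the last dose, the first three as a minimum. Section 11.2.2 collects "until 30 calendar days after discontinuation or completion of study treatment as defined by the study" and then, in the same sentence, also refers to the last dose.

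**The concern.** Which infusion was the last is known only afterwards. While a patient is on hold, nobody can say whether an AE arising on day 38 is on treatment. If dosing resumes, day 38 lies between two doses and the event is a TEAE. If the event makes the investigator stop treatment, the last dose stays where it was, the period has already closed on day 30, and the same event is not a TEAE. Classification then depends on what the event led to, and the events that drop out are those that ended treatment. The table most affected is the one meant to show them.

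Safety and tolerability are primary objectives of both parts, and TEAEs are a named endpoint in Table 1. Section 10.2 summarizes data by cohort and dose level, and Section 5.1.3 lets safety data from later cycles inform the final MTD. Section 5.1.1 plans escalation cohorts of 3 to 6 patients. In a dose group of that size, one omitted patient moves a rate by 1/6 = 17 to 1/3 = 33 percentage points.

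**Working it through.** Days are counted from the last infusion (day 0).

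**Inputs**
- Cycle length: 21 days (Section 7.1).
- Longest permitted delay past the planned date: 28 days (Section 6).
- End of on-treatment period: day 30, or the day before new anticancer therapy if that is earlier (Section 10.5.3).

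**The plan's own figure**
- Latest day on which re-dosing is still possible = cycle + delay = 21 + 28 = 49. This equals the 49 days that Table 2 states for Grade 1 ILD.

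**The gap**
- Days outside the period: 49 − 30 = 19, that is days 31 to 49.
- Delay at which the gap opens: 30 − 21 = 9, so any dose more than 9 days late.
- Share of the permitted delay that is uncovered: 19/28 = 68%. Share of the longest interval since the last dose: 19/49 = 39%. Both are shares of calendar days, not of patients or events.
- If the 2-day visit window on Day 1 is added to the limit, the last day becomes 51 and the gap 51 − 30 = 21 days.

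**Classification of a new AE by onset day and outcome**

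| Onset day | Patient later re-dosed | No further dose |
|---|---|---|
| 25 | TEAE | TEAE |
| 30 | TEAE | TEAE |
| 31 | TEAE | not a TEAE |
| 38 | TEAE | not a TEAE |
| 49 | TEAE | not a TEAE |

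**Where the excluded events can still appear**
- Related SAEs after the period: summarized (Section 10.5.3.1).
- Deaths and AEs of special interest (AESIs): summarized, with no stated limit to TEAEs (Section 10.5.3.1).
- Reason for stopping treatment: summarized in disposition (Section 10.5.1), and AE is one of the reasons (Section 3.3). This counts the stop but does not tabulate the event by term or grade.
- Laboratory values: summarized by scheduled time including the end-of-treatment visit, with Grade 3 or higher results listed (Section 10.5.3.2), but outside the shift table.
- All AEs: listed.

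Two groups are left with no AE summary table: non-serious events that are not AESIs, such as a new cytopenia, and non-fatal SAEs that are not AESIs and are judged unrelated.

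**The case against.** The strongest reply is that the affected set is small and partly visible elsewhere. Much of this stands.

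- *The AE that caused the hold is captured.* An event that prevented the planned dose will normally have begun by about day 21, so it is a TEAE and stays in the discontinuation table. The withdrawal rule in Section 6 concerns such persisting events. What drops out is a new event late in a hold.
- *Parallel displays exist.* A reader might infer that a late, non-serious ILD case would survive only in a listing. The documents do not support that: ILD/pneumonitis is an AESI (Section 11.11), it goes to an adjudication committee, and the AESI summary is not expressly limited to TEAEs.
- *Dose finding is protected.* DLTs are assessed on Days 1 to 21 of Cycle 1, so they are unaffected.
- *Thirty days from the last dose is conventional, and most of the protocol uses it.* A fixed exposure window is defensible in general. Here it is shorter than the interval within which the protocol itself allows re-dosing. Nor does the plan treat day-38 events as too late to matter, since it counts them for every re-dosed patient.
- *Section 7.4.1 expects the end-of-treatment visit within 30 days of the last dose.* That might suggest that no stop falls later, but footnote q provides for exactly that case.
- *A separate SAP may refine the definitions* (Sections 10.2 and 10.6). That is possible, but the only definition given is the one in Section 10.5.3.
- *The remedy does not remove all dependence on management.* An AE on day 38 would still be classified differently according to whether treatment was stopped on day 35 or on day 40. This is true. However, an AE that prompts the stop cannot begin after the decision, so the events of most concern are captured.

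**Conclusion.** The point holds in a narrow form, and the definition should be corrected. For a patient who is not re-dosed, new AEs with onset up to 19 days past the end of the period (days 31 to 49) are outside the TEAE, maximum-grade and TEAE-discontinuation tables. Laboratory values from those days are outside the shift table. The same findings in a re-dosed patient are inside. The condition is a dose more than 9 days late, a new onset after day 30, and no further infusion.

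Several stronger readings are tempting but unsupported:
- A patient is not held for 49 days. The hold is at most 28 days, and 49 is the time since the last infusion.
- Not every patient stopped after day 30 is affected, only one with a new onset after that day.
- The 39% and 68% figures are not a proportion of events lost, and the documents give no means of deriving a frequency.
- Holds in Table 2 are mainly for toxicity, so omissions would tend to flatter tolerability. A larger effect at higher doses is plausible but not shown.

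The conclusion assumes that Section 10.5.3 is applied as written and that AEs arising during a hold are recorded. If collection stopped at day 30, some would not reach the database at all.

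**What to change.** In Section 10.5.3, end the on-treatment period at the later of 30 days after the last dose and the date of permanent treatment discontinuation, still capped at the day before the first follow-up anticancer therapy. Apply that end date to the TEAE definition in 10.5.3.1 and the shift table in 10.5.3.2. Uncovered days before the stop fall from 19 to 0.

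Tabulate all AEs leading to permanent discontinuation, whatever their onset day.

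Align the collection wording in Sections 3.3, 7.1, 7.4.2, 11.2.2 and 11.4, so that AEs are collected at least to the new end date. The present mix of last dose and discontinuation matters. Counting 30 days from a stop on day 49 would run to day 79 (49 + 30), whereas counting from the last dose ends on day 30 at the minimum.

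Confirm that the eCRF records the date of permanent discontinuation. The documents describe an end-of-treatment visit after the decision, but do not say that the decision date is captured.

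The cost is one sentence of definition, one table, some wording changes and possibly one eCRF field. A few more TEAEs will be counted. The dose-delay rules are not touched.

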#### **10.5.3.1 Adverse Events and DLTs**

Safety will be assessed through the analysis of the reported incidence of treatment-emergent AEs (TEAEs). Treatment-emergent AEs are those with an onset date during the on-treatment period.

Adverse events will be graded according to NCI [CTCAE Version 5.0](#) and coded using the current version of Medical Dictionary for Regulatory Activities (MedDRA; <https://www.meddra.org/>).

DLTs in the DLT Evaluable Set will be listed and summarized.

Treatment-emergent AEs will be summarized using system organ class (SOC) and preferred term. In addition, treatment-emergent SAEs, TEAEs by maximum NCI CTCAE grade, and TEAEs associated with study treatment discontinuation, reduction or interruption will also be presented.

All AEs will be listed including, but not limited to, verbatim term, preferred term, SOC, NCI CTCAE grade, and relationship to study drug.

Deaths will be listed and summary tables will be generated.

SAEs starting or worsening after the on-treatment period, if reported as related to study treatment, will be summarized.

Adverse events of special interest (AESIs) once defined based on continued review of the safety profile of DS-6157a will also be summarized.

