## 2.4 Endpoints

**Table 1 Study Objectives and Corresponding Endpoints**

Primary Objectives:	Endpoint/Variable:

 
• Dose Escalation: To investigate the safety and tolerability and to determine MTD and RDE of DS-6157a
 
• Dose Expansion: To investigate the safety, tolerability, and efficacy of DS-6157a at RDE
 
	Dose-limiting toxicities (DLTs) Serious adverse events (SAEs) Treatment-emergent adverse events (TEAEs) Adverse event (AE) of special interest (AESIs) Chemistry/hematology laboratory parameters Physical examination Vital signs Electrocardiograms (ECGs) LVEF by echocardiogram (ECHO)/multi-gated acquisition scan (MUGA) Ophthalmologic findings Dose Expansion only: Objective response rate (ORR), duration of response (DoR), disease control rate (DCR), clinical benefit rate (CBR), time to response (TTR), progression-free survival (PFS), and best percent change in target lesion by RECIST Version 1.1

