## 7.2 Screening

At enrollment, each potential research patient will provide written informed consent  $\leq 28$  days prior to initiation of treatment and prior to starting any study-specific procedures. Upon signature of the ICF, patients will be assigned a unique patient number as enrollment (screening) occurs.

The study will allow re-screening for any patient who failed to meet eligibility criteria upon initial screening. The failed screening test(s) and the other screening results that are out of window relative to the start of the study treatment, and any other protocol-specified screening tests per the Medical Monitor's guidance, will be re-tested during re-screening. The initial screening information and the reason why the patient was ineligible for the initial evaluation will be recorded in the Screening Log.

The screening assessments described in the [Assessment Schedule](#) will be collected, reviewed, and determined whether acceptable by the site Principal Investigator or designee after obtaining informed consent prior to the initiation of treatment.

The following screening parameters should be recorded  $\leq 7$  days prior to initiation of treatment:

- Medical history and demographics
- Cancer history and prior cancer therapies
- Smoking history
- Physical examination (including height and weight) and skin assessments
- ECOG performance status
- Vital signs (blood pressure, SpO2, body temperature, and pulse rate)
- Triplicate ECGs
- Hematology (red blood cell [RBC] count, hemoglobin [Hb], hematocrit, reticulocytes, total white blood cell [WBC] count, absolute neutrophil count [ANC], absolute lymphocyte count, 5-part % differential [neutrophils, lymphocytes, monocytes, basophils, eosinophils], and platelet count)
- Biochemistry (sodium, potassium, phosphate, chloride, creatinine, calcium, venous bicarbonate HCO3 or carbon dioxide (CO2), albumin, total protein, AST, ALT, alkaline phosphatase [ALP], bilirubin [total {required}/fractionated {direct/indirect} bilirubin, if available], lactate dehydrogenase, serum glucose, creatinine kinase [CK: if CK is elevated, then CK-MB, CK-MM, troponin I, and myoglobin should be reactively tested, with further follow-up as clinically warranted], blood urea nitrogen [BUN] or urea, and serum uric acid)
- Urinalysis (Dipstick); if abnormal and clinically significant, the Investigator must order a microscopic analysis of the urine sediment
- Screening pregnancy test (serum)

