## **11.2 Recording and Reporting of Adverse Events**

### **11.2.1 Recording of Adverse Events**

All AEs, SAEs, and AESIs will be reported in the eCRF.

All events (serious and non-serious) must be reported with Investigator’s assessment of the event’s seriousness, severity, and causality to the study drug. A detailed narrative summarizing

*CONFIDENTIAL*

the course of the event, including its evaluation, treatment, and outcome must be provided. Specific or estimated dates of event onset, treatment, and resolution must be included when available. Medical history, concomitant medications, and laboratory data that are relevant to the event will also be summarized in the narrative. For fatal events, the narrative will state whether an autopsy was or will be performed and include the results if available. Source documents (including medical reports) will be retained at the study site and must not be submitted to the Sponsor for SAE reporting purposes.

Grade 3 or Grade 4 AEs ongoing at the discontinuation of the study drug will be monitored (including local laboratory tests when appropriate, see Section 3.3) until the AE is determined to be resolving or back to baseline.

Additional relevant information regarding the AESIs ILD/pneumonitis (Section 11.11), regardless of seriousness, is to be collected through the targeted questionnaires within the eCRF. Additional relevant information regarding the AESI infusion-related reaction (Section 11.11) is to be collected through the narrative form within the eCRF.

For broad surveillance of ILD/pneumonitis, a set of pre-defined list of preferred terms eligible for adjudication as described in the Event Adjudication Site Manual, is utilized for enhanced data collection.

Disease progression/worsening of the cancer will not be recorded as an AE on the Adverse Event eCRF. However, events associated with disease progression, such as clinical symptoms, may be recorded as AEs. Death due to disease progression should be recorded on the Death eCRF.

If the AE is serious, it must be reported immediately to Innovations Safety Department via electronic data capture (EDC). Other untoward events occurring in the framework of a clinical study are to be recorded as AEs (i.e., AEs that occur prior to assignment of study treatment that are related to a protocol-mandated intervention, including invasive procedures such as biopsies, medication washout, or no treatment run-in).

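### TEAEs are defined by onset date alone, so as written an AE entered between consent and first dose whose CTCAE grade rises on treatment is left out of the TEAE summaries

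*Combined protocol and SAP*

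**What the plan says.** The only TEAE definition is in Section 10.5.3.1: "Treatment-emergent AEs are those with an onset date during the on-treatment period". Section 10.5.3 gives the on-treatment period as "From the start of study treatment, to earlier of (30 days after the last dose of the study treatment" or, if sooner, the day before the first follow-up anticancer therapy.

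Recording starts before that period. Section 11.2.2 asks for "All AEs regardless of seriousness or relationship to DS-6157a treatment (called study treatment), spanning from the signing of the ICF". Under Section 7.2, "each potential research patient will provide written informed consent" no more than 28 days before treatment begins. Section 11.2.1 expects events in this interval. Its examples are "AEs that occur prior to assignment of study treatment that are related to a protocol-mandated intervention, including invasive procedures such as biopsies", followed by medication washout and a run-in without treatment.

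Section 10.5.3.1 then builds its summaries on the TEAE flag. TEAEs are tabulated by system organ class and preferred term and, in addition, "treatment-emergent SAEs, TEAEs by maximum NCI CTCAE grade, and TEAEs associated with study treatment discontinuation, reduction or interruption will also be presented". One sentence in that section does cover worsening, but only for "SAEs starting or worsening after the on-treatment period" that are reported as treatment-related.

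Table 1 lists TEAEs among the primary safety endpoints. Section 5.1.2 defines a DLT as a TEAE occurring in the 21-day evaluation period.

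**The concern.** A TEAE summary should show what became new or worse once treatment began. A rule that looks only at the onset date captures the new events and misses the worse ones when the AE record was opened before dosing.

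That can matter here because fresh pre-treatment biopsies are normally required and prior drugs are washed out, so AEs between consent and first dose are foreseeable. If such an event persists and its grade rises on treatment, the rise may be the most informative part of its course. Under the stated rule it appears in none of the TEAE tables, even if it becomes serious or leads to a dose reduction. Those tables are the main summary of a primary safety endpoint in a first-in-human study.

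**Working it through.** The documents state no count, rate or sample size for such events, so there is no figure to reproduce. The check applies the rule to a test case and then looks for any text that would change the result.

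**Test case (illustrative).** An AE is entered on Day -5 at Grade 1, does not resolve, and reaches Grade 3 on Day 10.

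1. Recorded as an AE? Yes. Day -5 is after consent, and Section 11.2.2 records all AEs from that point.
2. Onset in the on-treatment period? No. The period starts at first dose (Day 1), and Day -5 is earlier.
3. TEAE? No. Onset is the only criterion in Section 10.5.3.1.
4. Which summaries lose it? System organ class and preferred term, treatment-emergent SAEs (if it became serious), maximum grade, and discontinuation, reduction or interruption (if dosing changed). Section 6 bases dose changes on the worst preceding toxicity and requires them on the AE form. A resulting dose reduction would therefore be recorded against the event yet be missing from the table of TEAEs associated with reduction.
5. Where does it remain? In the listing of all AEs and, if it is a laboratory abnormality, in the shift table of Section 10.5.3.2.

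**Search for a rule that would change steps 2 or 3.**

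- Section 11.2.1 defines persistent and recurrent AEs. It does not mention a grade change, a new record or a new onset date.
- Section 11.7 makes a pre-existing medical condition an AE once it worsens. That addresses medical history, not an AE already entered after consent.
- The worsening clause in Section 10.5.3.1 applies only after the on-treatment period and only to related SAEs. Worsening within the period has no counterpart.
- Section 10.6 leaves safety definitions to the SAP. No separate SAP text is in the supplied documents.

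Nothing found changes the result.

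**Link to DLTs.** Section 5.1.2 opens by making a DLT a TEAE. Its exceptions then exempt Grade 3 hyponatremia of under 72 hours that arose from Grade 1 at baseline. That exemption is needed only if worsening from baseline could otherwise be a DLT. The AST/ALT criteria for patients with liver metastases likewise depend on the baseline level. If the baseline abnormality had been entered as an AE before dosing, the opening of 5.1.2 read with 10.5.3.1 would exclude it, while the exceptions imply that it can count. This is a tension in wording between the two sections.

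**The case against.** The strongest reply is that the gap is narrow and well covered. It concerns only AEs entered between consent and first dose, unresolved at dosing, that later rise in grade. Section 10.6 assigns definitions to the SAP, and an eCRF that opens a new record at each grade change would capture the worsening. All AEs are listed, deaths and AESIs are summarized without a stated TEAE restriction, and laboratory shifts are tabulated. Vital signs and ECGs are reported as change from baseline, and other safety findings have summary tables. SAEs are reported within 24 hours from consent onward. The study is descriptive, with no statistical testing.

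Most of this stands, and it limits the consequence. It does not put the event back into the TEAE tables: a listing is not a summary, and shift tables miss non-laboratory events. The SAP or eCRF remedy is possible, but the supplied text does not state it.

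Two stronger readings are tempting, and the documents support neither.

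- A reader might infer that worsening of any condition present at entry is lost, for example a chronic Grade 2 toxicity allowed under Section 3.2. Section 11.7 makes a pre-existing condition an AE only once it worsens, so no AE record exists before then and the natural onset is the worsening.
- A reader might infer that Cycle 1 DLTs will be missed and the dose-escalation model biased. The exceptions in Section 5.1.2 show that worsening from baseline is meant to be able to count. Sections 5.1.1 and 5.1.3 also bring overall safety data into dose and MTD decisions.

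**Conclusion.** The point holds in its narrow form. As the protocol is written, an AE entered after consent and before first dose, still present at dosing, whose CTCAE grade rises on treatment is not a TEAE and is absent from every TEAE summary in Section 10.5.3.1. This follows from a stated rule rather than from missing detail, and it sits oddly beside the worsening clause for later related SAEs.

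The size cannot be given. One affected patient changes a row by one over its denominator, but nothing in the documents indicates how many patients would be affected. The effect is probably limited, given the other displays.

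The conclusion assumes that a rise in grade does not open a new AE record with a new onset date, and that the SAP adds no worsening criterion. Either would remove the problem. The DLT issue is a wording conflict to reconcile, not evidence that DLTs will be lost.

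**What to change.** In Section 10.5.3.1 and in the SAP, define a TEAE as an AE with onset, or with worsening in CTCAE grade from its pre-dose state, during the on-treatment period, dated at the worsening. Give sites a matching eCRF instruction so that the date of worsening is available.

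Reconcile Sections 5.1.2 and 10.5.3.1 in the same amendment. Because 5.1.2 borrows the term TEAE, a changed definition carries into the DLT definition, so the text should say explicitly how a worsened pre-dose AE is classified for DLT purposes. No DLT rule is proposed here.

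The cost is one sentence in two documents, a cross-reference in 5.1.2 and a data-entry instruction. TEAE counts may rise slightly, and sites must record a worsening date.
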